Patients will be excluded if any of the following criteria are met:

- 1) delirium or dementia diagnosis,
- 2) unstable medical illness or clinically significant laboratory results,
- 3) history of clinically significant cardiovascular disease or electrocardiogram (EKG) findings, or medical conditions that put the patient at risk for possible cardiac side effects (e.g., requirement of cardiac pacemaker) or alter brain morphology (e.g., recent head trauma, post intracranial surgery, intracranial mass or bleed or unstable sleep apnea), or a blood pressure $>140/95$ mmHg at Screening,
- 4) history of multiple adverse drug reactions, (e.g., history of hives or anaphylaxis in response to a medication, severe intolerance and/or severe side effects to a medication), including hypersensitivity to ketamine,
- 5) current/past history of psychotic disorders, history of out-of-body feelings or derealization,
- 6) active substance use disorders (except nicotine and caffeine) within the past six months or past history of ketamine/PCP abuse (we will confirm this with collateral information from their doctor if necessary),
- 7) requirement of excluded medications that may interact with ketamine (see exclusionary medications list),
- 8) caffeine or nicotine use within 1 hour of psychophysiology testing, or alcohol use within 1 day of testing,
- 9) pregnancy, breastfeeding, or unacceptable means of birth control (females only)
- 10) clinically significant hearing impairment,
- 11) current serious suicidal or homicidal risk,
- 12) concurrent participation in other research studies involving medications or other treatments,
- 13) narrow angle glaucoma,
- 14) acute intermittent porphyria history,
- 15) history of seizures in the past 6 months, regardless of seizure type,
- 16) hyperthyroidism or untreated hypothyroidism,
- 17) airway instability or pulmonary disease with hypercarbia, or
- 18) current or past cubital or carpal tunnel syndrome.

IV. Participant Enrollment

We will enroll 58 depressed patients outpatients into the study.

Recruitment: 58 outpatients will be enrolled via response to flyers, advertisements, e-mails, participation in previous studies with an interest in participating in further research, and letters to providers. The DCRP has used these methods for over two decades with considerable success, receiving an average of over 35 phone calls/week.

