Retention: All patients are eligible to receive a free consultation at the DCRP immediately following the completion of all study materials. This care is supplemental to their ongoing care with their treating psychiatrist/doctor. The treating psychiatrist will be informed before any medications changes are considered.

Renumeration: All participants who complete all parts of the study will be paid \$200, and parking will be validated for the study visits. For patients that come in for the screening visit only, they will be renumerated \$20; parking will also be validated. The payment schedule for the other three visits is \$60 each.

Note, the probabilistic reward task is a monetary reward task. Patients will be told that their payment for this task, based on the money they win, will be included in their total payment for study participation.

Procedures for Informed Consent

[figure not shown]
Written informed consent will be obtained by a licensed physician from all patients before protocol-specific procedures begin. The investigator obtaining consent will explain in detail the protocol of the study, its purpose, and potential benefits to the society. Participants will be informed that they can choose to terminate the study at any time, for any reason.

Treatment Assignment and Randomization (If Applicable)

N/A; All participants will be assigned to open-label ketamine.

V. Study Procedures

Research Design Summary: The proposed research (Aims 1-3) will begin with a screening visit (Visit 1) and a medication stabilization period of ≥ 28 days (Phase I). In Phase II, 58 depressed patients meeting research criteria (specified above) will undergo baseline biomarker and psychometric assessments (Visit 2). One-to-two days later, they will receive an open-label infusion of subanesthetic intravenous ketamine (0.5mg/kg over 40 minutes), and will be monitored for 4 hours in the MGH Clinical Research Center (Visit 3). Visit 4, which will occur on the day after the ketamine infusion, will consist of the same biomarker and psychometric assessments from Visit 2 (see “Schema” for overall study outline):

Visits and Parameters to be Measured/Data to be Collected and When the Data is Collected

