Ketamine Administration and Monitoring: Ketamine is a glutamatergic receptor antagonist that has been administered to millions of patients worldwide as a general anesthetic, though its antidepressant mechanism of action (at sub-anesthetic doses) remains largely unknown. Although low-dose ketamine has been shown to have a favorable safety profile when given to depressed patients in several studies,(1, 24-27) there is a potential risk of adverse psychotomimetic, dissociative, and/or sympathomimetic events. Similar to previous studies showing efficacy and safety of intravenous ketamine in adults with mood disorders,(1, 45, 46) including studies completed at the MGH CRC (e.g., Protocol 2012P001042), ketamine will be administered at 0.5mg/kg over 40 minutes by a BLS and ACLS-certified, licensed physician at the MGH General Clinical Research Center. Patients will be monitored at the General Clinical Research Center by a medical doctor and trained nurse for changes in vital signs (i.e., heart rate, blood pressure, respiration, temperature, pulse ox, and sedation level) and for treatment-emergent side effects (i.e., as measured by the CADSS and BPRS) during administration and post-administration. Rescue medications, including intravenous labetalol, lorazepam, ondansetron, and haloperidol will be available in the event that unwanted side effects occur; participants requiring such interventions will be withdrawn from the study. PO ibuprofen and acetaminophen will also be available. The following parameters are specified in the order set for the CRC:

1. Oxygen 4 to 6 liters/min via face mask or nasal cannula PRN, SpO₂ <93% at bedside
2. Labetolol 2.5 mg IV push over 2 mins PRN BP ≥3 readings in a row of BP ≥ 160/100; may repeat every 2 to 5 mins X5. Given by MD/NP. Infusions will be stopped if BP ≥160/00 persists for more than 20 minutes. PRN for tachycardia >100 bpm; symptomatic tachycardia >100 bpm requires EKG.
3. Lorazepam 2mg IV push PRN severe agitation, attempting to pull out IV; May repeat every 2-5 minutes X 3. Given by MD/NP
4. Haloperidol 1-2mg IV push PRN delirium (not oriented to space and time, hallucinations, attempting to pull IV); May repeat every 10 minutes X 5. Given by MD/NP
5. Glycopyrrolate 0.1mg IV push PRN excessive salivary secretion; May repeat every 2-5 minutes X 3. Given by MD/NP
6. Ondansetron 4mg IV PRN severe nausea, may repeat x1 after 30 min if no effect.

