Testing of Hypotheses: Statistics and Data Analysis

Specific Aim #1: Objective and subjective measures of anxiety will be positively correlated with each other. A primary analysis will examine Pearson correlations between subjective measures of anxiety (i.e., the HDRS Anxiety-Somatization Factor Scale, HAM-A, and CUDOS-A) and eye-blink startle response. Similarly, we will examine correlations between subjective anxiety and reward responsiveness. We will analyze the data to ensure that linearity exists. If linearity does not exist, we will conduct comprehensive sub-analyses to find the best way to characterize the relationship of all data. For example, we will use covariates (e.g., clinical descriptors such as treatment failures) to determine their role in creating non-linearity.

Specific Aim #2: Greater psychophysiological and cognitive objective measures of anxiety will predict better antidepressant response to ketamine, regardless of subjective depression symptoms. We will use a nonlongitudinal linear regression model to assess the extent to which the combination of pre-treatment psychophysiological (e.g., anxiety-potentiated eye-blink startle) and cognitive reward processing (high versus low reward responsiveness) predict the antidepressant treatment response to ketamine (Visits 3 and 4). Antidepressant response to ketamine will be defined as a $\geq 50\%$ improvement in HDRS scores (primary dependent outcome measure).

Specific Aim #3: In ketamine responders, psychophysiological measurements will show a significantly larger decreases in magnitude compared to ketamine nonresponders; greater improvements will be seen in cognitive reward processing measures in ketamine responders. We will use longitudinal analyses (linear mixed effects random regression models) to analyze the effect of ketamine on

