the biomarkers. These models account for the correlation of observations from the same individual. For the change in startle magnitude post-ketamine, the model will include the change in startle magnitude as the outcome, and time (Visit 2 and 4) as the predictor. For the change in reward processing post-ketamine, the model will include the change in reward processing as the outcome, and time (Visit 2 and 4) as the predictor. The coefficient for the correlations in this model quantifies the rate of change in the psychophysiological and cognitive measures associated with a change in depressive symptoms. A coefficient significantly different from zero indicates that changes in the clinical measures of depression are associated with changes in psychophysiological and/or cognitive measures. We will also perform between-group comparisons of measurements for responders vs. nonresponders. All models will be fit using SAS software, $\alpha=0.05$, two-tailed.

Sample Size Determination:

The sample size for Aims #1 and #2 was calculated using the G*Power Sample Size calculator (Version 3.9.1.2; downloaded from <http://www.gpower.hhu.de>) and was based on findings from a *post-hoc* analysis of the antidepressant treatment response to ketamine in anxious versus nonanxious depressed patients, where anxious depression predicted a better response to open-labeled ketamine.(6) The anxious depression effect size (Cohen's *d*) reached its maximum of $d=0.76$ on Day 2 post-infusion. With this, for Aims #1 and #2, we estimate requiring 58 patients with power >0.8 , $r=0.35$ and an $\alpha=0.05$, two-tailed, in order to reject the null hypothesis that there will be no correlations with baseline psychophysiological and cognitive measures between ketamine responders and nonresponders. For Aim #3, a sample size of 58 would allow us to detect a moderately-large effect size (Cohen's $d\geq 0.75$) for between-group comparisons. In order to account for potential drop-outs, we will recruit 70.

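### Sections IV and V plan for 58 patients and Section VI for 70; 58 is the bare number needed for power, so following Sections IV and V leaves no drop-out allowance

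*Combined protocol and SAP*

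**What the plan says.** Section IV (Participant Enrollment) gives the number twice: "We will enroll 58 depressed patients outpatients into the study" and, in the paragraph labelled Recruitment, "58 outpatients will be enrolled via response to flyers". Section V (Research Design Summary) uses the same number for those reaching Visit 2: "In Phase II, 58 depressed patients meeting research criteria (specified above) will undergo baseline biomarker and psychometric assessments".

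Section VI (Sample Size Determination) presents 58 as the result of the power calculation. For Aims 1 and 2, "we estimate requiring 58 patients with power >0.8", at r=0.35 and two-sided alpha 0.05, based on d=0.76 from an earlier post hoc analysis. For Aim 3, "a sample size of 58 would allow us to detect a moderately-large effect size", namely d of at least 0.75; no power and no responder split are given. The paragraph ends: "In order to account for potential drop-outs, we will recruit 70".

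The plan also foresees losses once patients are in Phase II. Section V says of those given rescue medication that "participants requiring such interventions will be withdrawn from the study". It discontinues patients with serious adverse events during or after the infusion, and it lets patients leave at the shock work-up.

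For Aim 1, Section VI names the analysis: "A primary analysis will examine Pearson correlations between subjective measures of anxiety" and the eye-blink startle response.

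**The concern.** The same figure serves as the enrolment target in one place and as the number needed after losses in another. Staff who follow Section IV stop at 58 and lose the allowance that Section VI says is needed. Staff who follow Section VI exceed the Section IV number. The plan does not say whether 58 or 70 counts consented patients, patients entering Phase II, or completers, so a reader cannot tell which is intended.

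At stake is the power stated for the three aims. Aim 3 compares Visit 2 with Visit 4, and Aim 2 needs a depression rating after the infusion, so both are exposed to losses on or after the infusion day. Aim 1 uses baseline data and is affected only by losses before Visit 2 or at the shock work-up.

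**Working it through.** **Inputs.** From Section VI: N=58, r=0.35, d=0.76, two-sided alpha 0.05, d=0.75 for Aim 3, 70 recruited. From Sections IV and V: 58 enrolled, 58 entering Phase II. Drop-out and response rates are not in the documents; the values below are assumptions.

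**1. Reproducing 58.** Two-group t test, noncentrality d·√(n₁n₂/(n₁+n₂)), n₁+n₂−2 degrees of freedom, d=0.76:
- 28 per group: 0.76·√14 = 2.84, power 0.798
- 29 per group: 0.76·√14.5 = 2.89, power 0.812

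So 58 is the smallest equal-group total above 0.80, with no padding. The matching correlation is r = d/√(d²+4) = 0.76/√4.5776 = 0.355, which the plan rounds to 0.35. In the point-biserial model (noncentrality √N·r/√(1−r²), N−2 degrees of freedom), r=0.35 gives power 0.7985 at 58 and 0.8055 at 59. The plan's 58 therefore reproduces, exactly at d=0.76 and to rounding at r=0.35.

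**2. What 70 implies.** 1 − 58/70 = 12/70 = 17.1%. Recruiting 70 covers up to 12 losses, which fits 58 as the number left after drop-out.

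**3. Power if only 58 are enrolled** (point-biserial):

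| Assumed loss | Analysed | r=0.35 | r=0.355 |
|---|---|---|---|
| 0% | 58 | 0.80 (0.7985) | 0.81 |
| 5% | 55 | 0.78 | 0.79 |
| 10% | 52 | 0.75 | 0.77 |
| 17% | 48 | 0.72 | 0.73 |
| 20% | 46 | 0.70 | not computed |

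At r=0.355, 57 analysed gives 0.805 and 56 gives 0.798: one loss is tolerated, two are not. The 17% row puts the whole 58/70 allowance on the 58. Part of that allowance may be for Phase I, so Phase II losses alone could be smaller.

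**4. Enrolment needed to keep 58 analysed**, 58/(1−loss) rounded up: 62 at 5%, 65 at 10%, 69 at 15%, 73 at 20%.

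**5. Aim 1 with a full 58.** For a Pearson correlation between two normally distributed measures, power is 0.781 at r=0.35 (61 patients needed for 0.80) and 0.794 at r=0.355 (59 needed).

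**6. Aim 3 with a full 58, d=0.75.** Power by responder split, using the t-test formula of step 1: 0.801 at 29/29, 0.801 at 28/30, 0.784 at 23/35, 0.724 at 17/41.

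**The case against.** Section VI speaks of recruiting 70, and Section V's 58 is a count at Visit 2, after screening and at least 28 days of stable medication. One can read this coherently as 70 recruited and 58 reaching Phase II, in which case the allowance is in the plan and only definitions are missing. Phase II is short, three visits over four days with one infusion, so losses there may be few, and no document gives a rate. For Aim 2, Section VI mentions Visits 3 and 4 and the depression scale is given at every visit, so a patient who misses Visit 4 may still contribute. The plan also does not say that data from withdrawn patients are discarded. Finally, the Aim 1 shortfall is about 0.02, or 0.006 at the unrounded r.

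Part of this stands. The loss rates are assumptions, the effect of a small loss is modest, and the exposure of Aim 2 depends on which visit's rating is used. The coherent reading is not stated anywhere, however, and Section IV puts 58 in its own Recruitment paragraph. Even on that reading, 58 at Visit 2 leaves nothing for later withdrawals. Aim 3 cannot avoid this, because it needs both visits. The Aim 1 shortfall is small, but Section VI claims power above 0.8 for Aim 1 explicitly, and the analysis it names does not reach that figure with 58.

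**Conclusion.** The concern holds. The plan carries two unreconciled targets, and 58 is a minimum analysed number rather than an enrolment number with a margin. If Sections IV and V are followed, power at r=0.35 is about 0.80 with no loss, 0.78 at 5%, 0.75 at 10% and 0.72 at 17%. These figures are conditional on assumed losses and on the effect size taken from the post hoc analysis. Separately, and with no loss at all, Aim 1 has power of about 0.78 (0.79 at r=0.355) against the stated figure above 0.8. The Aim 3 effect size corresponds to about 80% power only if responders and nonresponders are close to equal in number. The conflict between the targets is certain; the loss of power is moderate. It should be corrected.

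**What to change.** - Use one target in Sections IV, V and VI. With the numbers already in the plan, this would be to enrol up to 70 so that at least 58 have both Visit 2 and Visit 4 data.
- Say whether each number counts consented patients, patients entering Phase II, or completers, and state the assumed drop-out, split between Phase I and Phase II if possible.
- If 58 is the true enrolment number, keep it and restate power for the expected completers.
- Restate Aim 1 power with 58 analysed as about 0.78 at r=0.35 (0.79 at r=0.355).
- For Aim 3, give the power that goes with d of at least 0.75 and say that it assumes a roughly even responder split.

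This is a text correction, and the price is slightly less favourable power figures. The 70 already stands in Section VI, so nothing is added to that number. Measured against Section V's 58, however, up to 12 more people could enter Phase II, which is why the text must say which patients the 70 counts.

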In addition, we will include a computer based pattern separation task at Visits 2 and 4. The pattern separation task is a high throughput behavioral task that captures the input-output transformation function characteristic of pattern separation processes. (33) For example, if you park your car in the same lot everyday, but not the same space, pattern separation is thought to be involved in the process of you finding your car everyday despite being in a different space; this may be dysfunctional in people with depression. In this task, patients are shown a series of every-day objects (e.g., a car, garden tool, food, etc.) and are asked to identify the objects as being indoor or outdoor objects. Immediately after this, a second part of the task is started in which the patients are shown another series of objects. They are asked to call the objects as "old" if they have seen the objects before in the task, "new," or "similar." As previously done by Stark and colleagues,(33) a third of the objects in the testing phase are "old", "similar" and "new". Identifying a "similar" object correctly conveys pattern separation, whereas, incorrectly identifying it as "old" conveys pattern completion. By plotting responses as a function of object similarity, we can generate an input-output transfer curve. This task will serve the purpose of rapid assessment of putative changes in pattern separation.

Psychometric Assessments: Self- and clinician-rated assessments will take place during the study. We will administer the following scales to all participants at all visits (Visits 1-4): the Hamilton Depression Rating Scale (HDRS) (the primary dependent outcome measure) is a 28-item validated clinician-administered scale that is widely used as an observational rating measure of depression presence and severity;(34) the Montgomery Asberg Depression Rating Scale (MADRS), a 15-item validated clinical-administered scale widely used for the assessment of depression (35); Hamilton Psychiatric Rating Scale for Anxiety (HAM-A) is a 14-item validated clinician-administered scale that is widely used as an observational rating measure of anxiety presence and severity;(36) Clinically Useful Depression Outcome Scale (for the DSM-5 Anxious Distress Specifier) (CUDOS-A) is a 22-item self-rated scale for the assessment of DSM-5 anxious distress;(37) Young Mania Rating Scale (YMRS) is an 11-item clinician-rated scale for the measurements of hypomanic/manic symptoms;(38) MGH Sexual Functioning Questionnaire (SFQ) is a 7-item self-rated scale for the assessment of sexual functioning; *Snaith-Hamilton Pleasure Scale* (SHAPS) is a 14-item self-report questionnaire for the assessment of anhedonia (please loss to previously pleasurable activities);(39)

We will administer the following to all participants at Visit 1 only (screening): *Mini-International Neuropsychiatric interview (M.I.N.I.)* to assess for the presence of depression;(40) the MGH Antidepressant Treatment History Questionnaire (ATRQ), a clinician-rated scale used to determine treatment resistance in depression;(41) the *Early Trauma Inventory Self Report-Short Form* (ETISR-SF), a 29-item self-report item on early trauma history,(42) the EHI (a self-reported measure of dominant handedness), and a demographics form.

We will administer the following scales to all participants during Visit 3 (ketamine administration) only: *Brief Psychiatric Rating Scale (BPRS)* is an 18-item clinician-administered scale for the assessment of psychotic symptom constructs;(43) *Clinician Administered Dissociative States Scale (CADSS)* is a 28-item clinician-administered scale for the assessment of dissociative symptoms.(44) BPRS and CADSS will be administered at baseline, +40 minutes, +80 minutes, and +120 minutes in reference to the start of the ketamine infusion.

Study clinicians at the DCRP will be responsible for administering all clinician-administered scales and assessments. Clinicians have been extensively trained in the use of the HDRS₂₈ by videotapes and live patient interviews.

Concomitant Medications and Adverse Events: Concomitant medications (dosage, start and stop dates) will be reviewed and recorded at all visits in the chart. Adverse events will be recorded at all visits on the Adverse Events Form.

Peripheral Blood Sample Genetics and Biomarkers: At Screening, one 10 mL blood sample, one 8-10mL blood sample, one 6-8 mL blood sample, and two 10mL blood samples will be collected; two 8-10mL blood samples will be collected and at Visits 3 and 4, to obtain DNA for possible pharmacogenetic and biomarker (e.g. cytokines, metabolites, etc.) studies. The PI will ensure that appropriate privacy and de-identification procedures are in place for the collection of biomaterials.

In order to collect iPS cells for future biomarkers and genetics studies, all subjects will be referred to participate in Protocol 2009P000238, "The Use of Human Skin Cells and Blood Derived Cells in the Creation of Cellular Models of Neuropsychiatric Disorders" (P.I.: [name])." Subjects' choice as whether or not to participate in 2009P000238 will have no bearing on their ability to participate in the current protocol.

Drug to be Used: Ketamine will be the only research drug used as part of the study.

Ketamine Administration and Monitoring: Ketamine is a glutamatergic receptor antagonist that has been administered to millions of patients worldwide as a general anesthetic, though its antidepressant mechanism of action (at sub-anesthetic doses) remains largely unknown. Although low-dose ketamine has been shown to have a favorable safety profile when given to depressed patients in several studies,(1, 24-27) there is a potential risk of adverse psychotomimetic, dissociative, and/or sympathomimetic events. Similar to previous studies showing efficacy and safety of intravenous ketamine in adults with mood disorders,(1, 45, 46) including studies completed at the MGH CRC (e.g., Protocol 2012P001042), ketamine will be administered at 0.5mg/kg over 40 minutes by a BLS and ACLS-certified, licensed physician at the MGH General Clinical Research Center. Patients will be monitored at the General Clinical Research Center by a medical doctor and trained nurse for changes in vital signs (i.e., heart rate, blood pressure, respiration, temperature, pulse ox, and sedation level) and for treatment-emergent side effects (i.e., as measured by the CADSS and BPRS) during administration and post-administration. Rescue medications, including intravenous labetalol, lorazepam, ondansetron, and haloperidol will be available in the event that unwanted side effects occur; participants requiring such interventions will be withdrawn from the study. PO ibuprofen and acetaminophen will also be available. The following parameters are specified in the order set for the CRC:

1. Oxygen 4 to 6 liters/min via face mask or nasal cannula PRN, SpO₂ <93% at bedside
2. Labetolol 2.5 mg IV push over 2 mins PRN BP ≥3 readings in a row of BP ≥ 160/100; may repeat every 2 to 5 mins X5. Given by MD/NP. Infusions will be stopped if BP ≥160/00 persists for more than 20 minutes. PRN for tachycardia >100 bpm; symptomatic tachycardia >100 bpm requires EKG.
3. Lorazepam 2mg IV push PRN severe agitation, attempting to pull out IV; May repeat every 2-5 minutes X 3. Given by MD/NP
4. Haloperidol 1-2mg IV push PRN delirium (not oriented to space and time, hallucinations, attempting to pull IV); May repeat every 10 minutes X 5. Given by MD/NP
5. Glycopyrrolate 0.1mg IV push PRN excessive salivary secretion; May repeat every 2-5 minutes X 3. Given by MD/NP
6. Ondansetron 4mg IV PRN severe nausea, may repeat x1 after 30 min if no effect.
7. Acetaminophen 325mg tablets, take 1 - 2 tablets PO PRN headache, may repeat x1 after 30 min
8. Ibuprofen 200mg tablets, take 2 tablets PO PRN headache, may repeat x1 after 30 min

Research staff will be responsible for administering scales and for monitoring side effects. In order to minimize external stimuli, ketamine administration will occur in a room with low lighting and minimal noise throughout the administration, as well as during the monitoring period. Participants will be given a small snack 2 hours after the end of the ketamine infusion.

Discharge: After the ketamine infusion, if medically stable (as deemed by a board-certified physician study investigator), participants will be discharged home with a responsible family member or other adult caretaker. Discharge home will be based on criteria established by the MGH Department of Anesthesia practices for discharge from the hospital following ambulatory surgery. The participant must have stable vital signs, be able to respond appropriately to normal commands, be pain free, be free from any nausea and vomiting, and have no bleeding from the intravenous sites. Participants must be able to walk unassisted and have an accompanying adult to escort them home. Participants will be advised not to return to work and against driving or operating heavy equipment for 24 hours.

Medication Transport and Storage

The MGH Research Pharmacy and MGH CRC will store medications, including ancillary medications.

Devices to be Used

N/A

Procedures/Surgical Intervention

N/A

VI. Biostatistical Analysis

Specific Data Variables to be Collected

As described above, we will administer the following scales at all visits (Visits 1-4): HDRS, MADRS, HAM-A, CUDOS-A, YMRS, SFQ, and SHAPS.

We will administer the following at Visit 1 only (screening): M.I.N.I., ATRQ, and ETISR-SF.

We will administer the following scales during Visit 3 only (ketamine): BPRS and CADSS at baseline, +40 minutes, +80 minutes, and +120 minutes in relationship to the time of ketamine infusion.

Vital Signs will be recorded once at Visit 1 (the screening visit), and again at Visit 3 at baseline, +0 minutes, +5, +10, +15, +20, +30, +40, +60, +90, +120, +180 minutes in relationship to the time of ketamine infusion.

Study Endpoint

Primary clinical endpoint is change in the HDRS₂₈ total score. Scores that decrease by $\geq 50\%$ from baseline will be considered "response."

Specific Statistical Methods

Testing of Hypotheses: Statistics and Data Analysis

Specific Aim #1: Objective and subjective measures of anxiety will be positively correlated with each other. A primary analysis will examine Pearson correlations between subjective measures of anxiety (i.e., the HDRS Anxiety-Somatization Factor Scale, HAM-A, and CUDOS-A) and eye-blink startle response. Similarly, we will examine correlations between subjective anxiety and reward responsiveness. We will analyze the data to ensure that linearity exists. If linearity does not exist, we will conduct comprehensive sub-analyses to find the best way to characterize the relationship of all data. For example, we will use covariates (e.g., clinical descriptors such as treatment failures) to determine their role in creating non-linearity.

Specific Aim #2: Greater psychophysiological and cognitive objective measures of anxiety will predict better antidepressant response to ketamine, regardless of subjective depression symptoms. We will use a nonlongitudinal linear regression model to assess the extent to which the combination of pre-treatment psychophysiological (e.g., anxiety-potentiated eye-blink startle) and cognitive reward processing (high versus low reward responsiveness) predict the antidepressant treatment response to ketamine (Visits 3 and 4). Antidepressant response to ketamine will be defined as a $\geq 50\%$ improvement in HDRS scores (primary dependent outcome measure).

Specific Aim #3: In ketamine responders, psychophysiological measurements will show a significantly larger decreases in magnitude compared to ketamine nonresponders; greater improvements will be seen in cognitive reward processing measures in ketamine responders. We will use longitudinal analyses (linear mixed effects random regression models) to analyze the effect of ketamine on

the biomarkers. These models account for the correlation of observations from the same individual. For the change in startle magnitude post-ketamine, the model will include the change in startle magnitude as the outcome, and time (Visit 2 and 4) as the predictor. For the change in reward processing post-ketamine, the model will include the change in reward processing as the outcome, and time (Visit 2 and 4) as the predictor. The coefficient for the correlations in this model quantifies the rate of change in the psychophysiological and cognitive measures associated with a change in depressive symptoms. A coefficient significantly different from zero indicates that changes in the clinical measures of depression are associated with changes in psychophysiological and/or cognitive measures. We will also perform between-group comparisons of measurements for responders vs. nonresponders. All models will be fit using SAS software, $\alpha=0.05$, two-tailed.

Sample Size Determination:

The sample size for Aims #1 and #2 was calculated using the G*Power Sample Size calculator (Version 3.9.1.2; downloaded from <http://www.gpower.hhu.de>) and was based on findings from a *post-hoc* analysis of the antidepressant treatment response to ketamine in anxious versus nonanxious depressed patients, where anxious depression predicted a better response to open-labeled ketamine.(6) The anxious depression effect size (Cohen's *d*) reached its maximum of $d=0.76$ on Day 2 post-infusion. With this, for Aims #1 and #2, we estimate requiring 58 patients with power >0.8 , $r=0.35$ and an $\alpha=0.05$, two-tailed, in order to reject the null hypothesis that there will be no correlations with baseline psychophysiological and cognitive measures between ketamine responders and nonresponders. For Aim #3, a sample size of 58 would allow us to detect a moderately-large effect size (Cohen's $d\geq 0.75$) for between-group comparisons. In order to account for potential drop-outs, we will recruit 70.

Expected Outcomes/Results: We expect that subjective and objective measures of anxiety will be at least moderately correlated in patients with mood dysregulation. Further, we predict that patients with higher pre-treatment levels of objective anxiety, as measured by psychophysiological and cognitive assessments, will have significantly greater antidepressant responses to ketamine, compared to patients with lower pre-treatment objective anxiety. These results will significantly contribute to the paucity of information regarding biomarkers of diagnosis and antidepressant response and provide insight into the anxiety and reward neurocircuitry that could contribute to the pathophysiology of anxious depression.

VII: Risks and Discomforts

Complications of Procedures

Safety: At any time during the study, participants, family members, and treating psychiatrist will be encouraged to contact the principal investigator via phone or pager in the case of adverse events or worsening symptoms. The treating psychiatrist will be immediately notified of any concerns.

Drug Side Effects and Toxicities

Ketamine: Ketamine is a relatively commonly used anesthetic in both veterinary and human medicine. Although it has a good safety profile overall, ketamine has documented sympathomimetic activity that may result in mild to moderate increases in heart rate, blood pressure, and cardiac output, though this activity is generally short-lived.(47) Findings from previous research on single- and repeated-dose intravenous ketamine for treating depression have provided evidence that the autonomic changes that may occur during the active administration (i.e., elevated blood pressure, pulse) return to normal shortly after the infusion stops, with no clinically significant sequelae.(48, 49) Other possible side effects reported during ketamine infusion include arrhythmia, increased salivation, increased bronchial secretions, horizontal nystagmus, euphoria and hallucinations. Nystagmus may persist for a period after the ketamine infusion has terminated.

Rare side effects are allergic reactions (skin rash), pain at site of injection, increased intraocular pressure, ulcerations and inflammation in the bladder (reported in ketamine abusers). Ketamine is a controlled substance and has the potential for abuse and dependence, in particular in participants with history of drug abuse. Participants with history of substance abuse or dependence in the previous year will be excluded.

In light of ketamine's relatively good safety profile, all participants will be medically screened (including EKG and vital signs) prior to entering the active treatment portion of the study, to ensure healthy baseline general and cardiac functioning. In addition, as ketamine is an anesthetic that may result in respiratory depression, participants will be excluded from the study if they require sedatives or opiates. During the

administration, a medical doctor will remain in the room with a research nurse, the research assistant, and the patient, and vital signs will be monitored every 5 minutes during the 40 minutes of administration. Any concerning changes will be managed by the physicians. Criteria for discontinuation include ≥ 3 readings in a row of systolic BP ≥ 180 mmHg or diastolic BP ≥ 110 mmHg, HR ≥ 110 bpm, or symptomatic elevations in blood pressure (i.e., new onset headache, chest pain, or shortness of breath). Furthermore, the physician may choose to stop the infusion at any time if he/she believes it is in the best interest of the participant, based upon his/her clinical judgment.

Participants will stay at the General Clinical Research Center (GCRC) for up to 4 hours following the start of the administration, and will be monitored for psychotomimetic, dissociative, and sympathomimetic side effects during this time. Afterwards, they will be discharged home in the care of a responsible adult family member or caretaker after completing rating scales with the study physicians. If participants experience adverse events at home, they will be referred for evaluation at the nearest emergency department. These instructions will also be provided to the responsible adult escort prior to discharge. The participant's individual insurance plan will be responsible for covering this visit.

Prior to informed consent, potential participants will be informed of alternatives to research, and will be provided with the option to seek further psychopharmacological or psychotherapy-based interventions.

Electric Shocks

The electric shocks that participants receive will be self-selected to be highly annoying, but not painful. Subjects may stop the electric shocks at any time. The stimulator is manufactured by Digitimer. It is inspected annually by biomedical engineering under the auspices of Partners Human Research Committee (PHRC), who have affirmed compliance with safety regulation. The stimulator has been used in similar experiments across institutions, including the National Institute of Mental Health (NIMH), and has been approved by their IRB for use in humans.

Psychosocial (non-medical) Risks

Privacy: As per standard DCRP procedures, study data is recorded using standard forms. All data will be stored in locked cabinets. For statistical analysis, only study IDs will be used as identifiers. Separate folders with unblinded information (e.g., patient name) will be kept in a locked cabinet in a separate office to ensure the blind.

Safety Risk

Though patients with severe suicidal ideation will be excluded from the study at screening, any patient who, based on the investigator's judgment, is judged to present with an imminent risk of suicide will be discontinued from the study and referred to a local emergency room for further evaluation.

VIII: Potential Benefits

To Participating Individuals and Society

The patients participating to the study may feel better, if for only a brief period of time. Some may not receive any direct benefit. The results of this study may lead to improved understanding of the neurobiology of depression, as well as the biomarkers for diagnosis and treating depression. Furthermore, the results from this study may lay the groundwork for future studies into the mechanism of action of ketamine's antidepressant effects, as well as using neurobiology to subtype depression.

IX: Monitoring and Quality Assurance

Because this study is a physiological study of biomarkers, as opposed to a clinical trial, the principal investigator and co-investigators will be responsible for monitoring and quality assurance of the study. In conjunction with the research assistants, weekly meetings will be held and documented. Current participants in the study will be discussed at each meeting, and charts will be reviewed for completeness.

